**Effect of in vitro fertilisation (IVF) hormonal
therapy on metabolic, endocrine and
inflammatory status in IVF-conceived
pregnancy**

NCT03426228

Chapter 1: Aim of the study and Objectives

1. To explore the short-term effects of IVF hormonal therapy on maternal metabolic and inflammatory status, including:
 - i. Risk of glucose intolerance and insulin resistance
 - ii. Risk of other metabolic, endocrine and inflammatory disturbances (including lipid profile, gut microflora and thyroid function)
2. To identify possible early predictors of GDM and other metabolic-related adverse outcomes in IVF-conceived pregnancies.

Chapter 2: General Methods

2.1. Ethics and Consents

Approval to conduct the study was first granted by the University of Warwick's Biomedical and Scientific Research Ethics Sub-Committee (BSREC). The study protocol was also reviewed by the two main health authorities in the UAE.

2.2. Study Design

The presented study is a longitudinal quantitative cohort study (non-experimental), whereby blood samples were collected at different stages during IVF therapy.

2.3. Study Setting

The study took place at in three fertility clinics in the UAE. At the clinics, pre- and post-fertility treatments and in-house obstetric facilities are provided, including blood tests, scans, IVF procedures and in-house genetic testing. Most patients are followed up to the point of delivery.

2.4. Study Population

- **Pregnant group:** received IVF therapy and tested positive for pregnancy at 4 weeks, and continued taking IVF hormonal therapy until 12 weeks of pregnancy.
- **Non-pregnant:** received IVF therapy and tested negative for pregnancy at 4 weeks, and stopped taking IVF hormonal therapy at that point.

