2.7. Blood Tests

A trained nurse was in charge of measuring anthropometrics and clinical parameters (e.g. weight and blood pressure), in addition to taking fasting blood samples. The socio-demographics, medical and pregnancy histories of each patient

were recorded in their file. Blood tests were conducted at in the phlebotomy room and transferred to the lab (in-house) for analysis. Tests results were available on the clinics internal server at the end of each day.

Table 1: List of Blood Tests at Each Stage of the Study

Type of Tests	Phase 1- Baseline (Start IVF treatment)	Phase 2- Week 2 (Egg retrieval)	Phase 3- Week 4 (β - HCG test)	Phase 4- Week 12 (Final)
Female reproductive hormones: FSH, LH, oestrogen, progesterone	✓	✓	✓	
HbA1c	✓			✓
Fasting glucose	✓	✓	✓	✓
Fasting insulin	✓	✓	✓	✓
TSH	✓			✓
Fasting lipid profile	✓			✓
Adiponectin	✓			✓
LBP	✓			✓
β -HCG pregnancy	✓		✓	
Body weight	✓			✓

*Green highlight represents stage where non-pregnant vs. pregnant women groups were distinguished; FSH: follicle-stimulating hormones; LH: luteinizing hormone; HbA1c: glycated haemoglobin A1c; TSH: thyroid-stimulating hormone; LBP: lipopolysaccharide binding protein; β -HCG: beta-human chorionic gonadotrophin

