Appendix 2. Participants Study Tests

Effects of fertility drugs on glucose homeostasis, and other metabolic parameters on patients undergoing In Vitro Fertilisation (IVF) [NCT03426228](#)

IVF MEDICATION & METABOLIC PARAMETERS				
Baseline	Week2	Week 2	Week 4	Week 12
Start IVF Therapy	Pre-OPU	Embryo Transfer	+/- β -HCG	Final
A1C Fasting glucose Serum insulin Lipid profile Hormonal Profile (AMH, LH, FSH, progesterone, oestrogen) TSH LBP Adiponectin	Fasting glucose Serum insulin Hormonal profile (LH, progesterone, oestrogen)	Hormonal Profile (progesterone, oestrogen)	Fasting glucose Serum insulin Hormonal profile (progesterone, oestrogen, β -HCG)	HbA1c Fasting glucose Serum insulin Lipid profile TSH LBP Adiponectin

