**Effect of in vitro fertilisation (IVF) hormonal therapy
on metabolic, endocrine and inflammatory status in
IVF-conceived pregnancy**

NCT03426228

Statistical Analysis

1. Effects of IVF Therapy

Data analysis was performed with the Statistical Package for the Social Sciences (SPSS) software version 21.0 for Windows (SPSS, Chicago, IL). Parameters normality was confirmed with the Shapiro-Wilk test. Non-parametric Wilcoxon test for two related samples was conducted to assess changes at baseline vs. post-IVF treatment (12 weeks) within groups (pregnant or non-pregnant). Non-parametric Mann-Whitney U test for two independent samples was used to compare the two groups pregnant vs. non-pregnant, at baseline and at 12 weeks. Bivariate correlation was used to determine correlations between the different anthropometric and metabolic parameters at week 12. Data from the two groups were analysed separately. Linear regression was used for assessment of association of change in glucose level at 12 weeks (dependent variable) with change in other anthropometric and biochemical parameters, separately for each group. Changes in glucose and insulin levels (and the resulting HOMA-IR) throughout IVF therapy (baseline, 2, 4 and 12 weeks) were determined with the mixed model for repeated measures test. Significance level was set at $p < 0.05$ and 95% confidence interval.

2. Anthropometrics and Biomarkers of Gestational Diabetes Mellitus (GDM)

In the pregnant group, the Mann-Whitney U test for two independent samples was used to compare data at baseline with 12 weeks, for comparison between women who later developed GDM to the non-GDM group. Changes at baseline, 4 and at 12 weeks were assessed by non-parametric Wilcoxon test (two related samples) within groups (future GDM or non-future GDM women). Predictors of GDM were assessed using binary logistic regression, adjusting for the following variables: age and history of PCOS.

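### After week 4 pregnancy and continued IVF therapy coincide, so the week-12 group test, the pregnant group's week-12 change and the mixed model's pregnant-group changes cannot isolate a therapy effect, and the SAP does not name the early changes that come closest.

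*Protocol*

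**What the plan says.** Objective 1 (Protocol Chapter 1) concerns the short-term effects of IVF hormonal therapy on maternal metabolic and inflammatory status. Protocol 2.4 forms two groups from the week-4 pregnancy test. Women testing positive continued therapy; the others "tested negative for pregnancy at 4 weeks, and stopped taking IVF hormonal therapy at that point". The protocol describes no untreated group, no pregnant group that stopped, and no non-pregnant group that continued.

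SAP section 1 (Effects of IVF Therapy) plans:

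- Mann-Whitney tests to "compare the two groups pregnant vs. non-pregnant, at baseline and at 12 weeks".
- Wilcoxon tests of "changes at baseline vs. post-IVF treatment (12 weeks) within groups (pregnant or non-pregnant").
- Correlations at week 12, and a linear regression of the week-12 glucose change. Next to these stands the sentence "Data from the two groups were analysed separately".
- A mixed model for glucose, insulin and HOMA-IR "throughout IVF therapy (baseline, 2, 4 and 12 weeks"). No group term, interaction or specific contrast is given.

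Table 1 in Protocol 2.7 shows glucose and insulin at all four phases. HbA1c, TSH, lipids, adiponectin, LBP and body weight are measured only at baseline and week 12. Appendix 2 lists "Fasting glucose Serum insulin Hormonal profile (LH, progesterone, oestrogen") in its week-2 Pre-OPU column, ahead of the embryo-transfer column. Protocol 2.6 labels the week-2 visit as egg retrieval.

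**The concern.** The SAP heading and Objective 1 both name therapy as the effect of interest. A reader will take a significant week-12 difference, or a significant pregnant-group change, as evidence about therapy. Pregnancy itself may change these markers, and the definition of the groups leaves no way to remove that contribution at week 12. A pregnancy effect could be credited to therapy, or opposite effects could cancel and hide a real one. Meanwhile the changes that come closest to answering Objective 1 fall within the mixed model, but nothing marks them as the therapy contrasts.

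**Working it through.** The documents give no sample size, effect size or SD, so there is no planned figure to reproduce. The main check is whether the effects can be identified at all.

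**Step 1. Cell means.** From Protocol 2.4 and 2.6, write the expected value in each group at each visit. Let g be the baseline group difference, T2 and T4 the therapy effects at weeks 2 and 4, G4 and G12 the pregnancy effects at weeks 4 and 12, R what remains at week 12 of therapy up to week 4 (including time drift), and C the effect of continuing therapy after week 4.

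| Group | Baseline | Week 2 | Week 4 | Week 12 |
|---|---|---|---|---|
| Pregnant | μ + g | μ + g + T2 | μ + g + T4 + G4 | μ + g + R + C + G12 |
| Non-pregnant | μ | μ + T2 | μ + T4 | μ + R |

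**Step 2. What each analysis estimates.**

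- Pregnant minus non-pregnant at week 12: g + C + G12.
- Pregnant, baseline to week 12 (Wilcoxon or mixed model): R + C + G12.
- Pregnant, baseline to week 4 (mixed model): T4 + G4.
- Non-pregnant, baseline to week 12: R. This is free of pregnancy but measured 12 − 4 = 8 weeks after stopping, if both weeks are on one clock.
- Baseline to week 2, either group: T2.
- Non-pregnant, baseline to week 4: T4.
- Mixed model without a group term, baseline to week 12: R + p(C + G12), with p the proportion pregnant. This mixes pregnant women with women who have stopped.

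**Step 3. Rank.** These 8 cells and 8 parameters give a design matrix of rank 7. C and G12 are the only parameters that cannot be estimated; their sum can. T2 and T4 are estimable, but only because the table has no separate time effect at weeks 2 and 4. Adding visit effects at weeks 2, 4 and 12 gives 11 parameters and still rank 7, and then no therapy effect is estimable. The early contrasts therefore depend on assuming no time or cycle effect.

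**Step 4. Extent.** Per outcome, SAP section 1 has 2 Wilcoxon tests (one per group) and 2 Mann-Whitney tests (baseline and week 12); 2 of these 4 are affected. If all 8 metabolic, inflammatory and weight rows of Table 1 are tested, that is 8 × 2 = 16 of 8 × 4 = 32 tests, counting the lipid profile once and leaving out HOMA-IR. Only 2 of the 8 rows (glucose, insulin) have samples at weeks 2 and 4; the other 6 do not.

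**Step 5. Illustration.** Assumed: normal data, equal baselines, therapy effect zero, pregnancy effect d in SD units, n women per group, two-sided 0.05, and within-woman correlation 0.5, so that the change has SD 1. With m = 3n/π for the rank tests, and ignoring the negligible opposite tail:

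- Mann-Whitney: P ≈ Φ(d√(m/2) − 1.96)
- Wilcoxon: P ≈ Φ(d√m − 1.96)

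For n = 50 and d = 0.5, m = 47.75. Mann-Whitney: Φ(0.5 × 4.886 − 1.96) = Φ(0.483) = 0.685. Wilcoxon: Φ(0.5 × 6.910 − 1.96) = Φ(1.495) = 0.933.

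| n per group | Mann-Whitney, d = 0.3 / 0.5 / 0.8 | Wilcoxon, d = 0.3 / 0.5 / 0.8 |
|---|---|---|
| 30 | 0.206 / 0.473 / 0.857 | 0.362 / 0.763 / 0.990 |
| 50 | 0.311 / 0.685 / 0.974 | 0.545 / 0.933 / >0.99 |
| 100 | 0.545 / 0.933 / >0.99 | 0.834 / 0.998 / >0.99 |

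Simulation agrees to within 0.04 (0.664 and 0.934 at n = 50, d = 0.5). If therapy and pregnancy effects are equal and opposite, both rates fall to about 0.05.

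**The case against.** The title refers to IVF-conceived pregnancy and the objective is exploratory, so the target may be the combined state of being pregnant after IVF. For that target the week-12 tests are usable. This stands, but the SAP does not say so, and its heading names therapy.

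The SAP also does not ignore the early visits. The mixed model includes weeks 2 and 4. A visit-only fit would give baseline to week 2 directly with complete data. If the sentence on separate analysis covers the mixed model, baseline to week 4 in non-pregnant women is already a visit effect of that fit. This stands as well: a reader might infer that no early analysis was planned, and the documents do not support that. What is missing is that these changes are named as the therapy contrasts, and that the scope of the sentence is made clear.

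The early contrasts have no untreated comparator. That is correct: they are before-after changes and do not establish a therapy effect.

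Finally, the rates in the illustration are ordinary power for an assumed pregnancy effect. A reader might take them for type I error inflation. They are not: when the groups truly differ, rejecting equality is right. The error lies in attributing the difference to therapy.

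**Conclusion.** The point holds in a limited form. The week-12 Mann-Whitney test, the pregnant-group Wilcoxon test and the mixed model's pregnant-group changes at weeks 4 and 12 cannot separate therapy from pregnancy. At week 12 this follows from the group definitions alone, and no choice of test removes it. It holds whether therapy ended at or one week before the week-12 sample, because the longer exposure goes with pregnancy either way.

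A reader might infer that all of SAP section 1 is compromised. It is not. The baseline comparison is made as therapy starts. The non-pregnant Wilcoxon test is free of pregnancy, though measured after stopping. The correlation and regression examine associations within each group and make no group comparison, although the pregnant-group regression takes the same composite glucose change as its outcome.

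A reader might also infer that naming the early contrasts restores a therapy effect for every marker. It does so for none beyond glucose, insulin and HOMA-IR, and for those only if there is no time or cycle effect. It says nothing about therapy after week 4. The identification result needs no assumed numbers; the rejection rates rest wholly on the inputs stated with them. This should be fixed, but the tests remain usable once correctly labelled.

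**What to change.** In SAP section 1:

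1. Specify the mixed model with group (by the week-4 test), visit and group-by-visit, and say whether the sentence on separate analysis applies to it.
2. Report, with 95% confidence intervals, as the closest available on-therapy estimates for glucose, insulin and HOMA-IR: (i) baseline to week 2 in all women, averaging the groups by their observed proportions; (ii) baseline to week 4 in women testing negative. The SAP is written in the past tense ("Data analysis was performed with the Statistical Package for the Social Sciences (SPSS")), so label both post hoc if they are named after the data were seen.
3. State that both are uncontrolled and assume no time or cycle effect. Contrast (ii) also assumes no egg-retrieval effect and is conditional on a negative test. Contrast (i) needs the egg-retrieval assumption only if the week-2 sample was not taken before retrieval; Protocol 2.6 and Appendix 2 must be reconciled on this.
4. Describe the week-12 group difference as pregnancy plus continued therapy plus any pre-existing difference between groups defined by outcome. Report it as change from baseline, or adjusted for baseline, where baseline was measured. Describe the pregnant-group week-12 change as pregnancy plus all therapy received plus time, and the non-pregnant week-12 change as about 8 weeks after stopping.
5. Draw no therapy-specific conclusion for HbA1c, TSH, lipids, adiponectin, LBP or weight.
6. Reconcile Protocol 2.4, Protocol 2.6 and SAP section 1 on therapy status and time scale at the week-12 sample. Protocol 2.4 and 2.6 differ on when therapy ended, and the SAP treats week 12 both as after treatment and as part of therapy.

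The cost is wording and two contrasts from samples and a model already planned. The downside is narrower therapy claims and, if applicable, the post hoc label.

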2.5. Sampling Technique

The non-probability convenience sampling method was used to recruit participants for the study. Patients who were to start a fresh IVF treatment at any of the IVF Clinic branches and meeting the inclusion criteria were eligible to participate.

2.6. Study Protocol

After an overnight fast of 8 hours, there was collection of 10 ml of blood at four pre-defined time points during the IVF protocol:

1. **Phase 1** – At baseline, egg maturation (starting IVF therapy)
2. **Phase 2** – Week 2 – Egg retrieval (OPU procedure)
3. **Phase 3** – Week 4 – At pregnancy test (β -HCG test)
4. **Phase 4** – Week 12 (one week after completing IVF hormonal therapy for pregnant group).

2.7. Blood Tests

A trained nurse was in charge of measuring anthropometrics and clinical parameters (e.g. weight and blood pressure), in addition to taking fasting blood samples. The socio-demographics, medical and pregnancy histories of each patient

were recorded in their file. Blood tests were conducted at in the phlebotomy room and transferred to the lab (in-house) for analysis. Tests results were available on the clinics internal server at the end of each day.

Table 1: List of Blood Tests at Each Stage of the Study

Type of Tests	Phase 1- Baseline (Start IVF treatment)	Phase 2- Week 2 (Egg retrieval)	Phase 3- Week 4 (β - HCG test)	Phase 4- Week 12 (Final)
Female reproductive hormones: FSH, LH, oestrogen, progesterone	✓	✓	✓	
HbA1c	✓			✓
Fasting glucose	✓	✓	✓	✓
Fasting insulin	✓	✓	✓	✓
TSH	✓			✓
Fasting lipid profile	✓			✓
Adiponectin	✓			✓
LBP	✓			✓
β -HCG pregnancy	✓		✓	
Body weight	✓			✓

*Green highlight represents stage where non-pregnant vs. pregnant women groups were distinguished; FSH: follicle-stimulating hormones; LH: luteinizing hormone; HbA1c: glycated haemoglobin A1c; TSH: thyroid-stimulating hormone; LBP: lipopolysaccharide binding protein; β -HCG: beta-human chorionic gonadotrophin

Appendix 1. Anthropometrics and Medical History Questionnaire

Effects of fertility drugs on glucose homeostasis, and other metabolic parameters on patients undergoing In Vitro Fertilisation (IVF) [NCT03426228](#)

Subject Name:

Telephone No:

E-mail:

Age	
Height	
Weight	
BMI	
Nationality	
Smoking	
Parity	

Past Illness and Surgeries

Drug History

Family History

Women Health

Cycle:	Regular	Irregular
--------	---------	-----------

History of GDM:
Previous IVF trials:

Blood Analysis

Type	Level/ Unit	Frequency
Fasting glucose		4 times
Serum insulin		4 times
Lipid profile		Twice
FSH, LH		4 times
Oestrogen, Progesterone		4 times
Beta-HCG		Once

Appendix 2. Participants Study Tests

Effects of fertility drugs on glucose homeostasis, and other metabolic parameters on patients undergoing In Vitro Fertilisation (IVF) [NCT03426228](#)

IVF MEDICATION & METABOLIC PARAMETERS				
Baseline	Week2	Week 2	Week 4	Week 12
Start IVF Therapy	Pre-OPU	Embryo Transfer	+/- β -HCG	Final
A1C Fasting glucose Serum insulin Lipid profile Hormonal Profile (AMH, LH, FSH, progesterone, oestrogen) TSH LBP Adiponectin	Fasting glucose Serum insulin Hormonal profile (LH, progesterone, oestrogen)	Hormonal Profile (progesterone, oestrogen)	Fasting glucose Serum insulin Hormonal profile (progesterone, oestrogen, β -HCG)	HbA1c Fasting glucose Serum insulin Lipid profile TSH LBP Adiponectin

**Effect of in vitro fertilisation (IVF) hormonal therapy
on metabolic, endocrine and inflammatory status in
IVF-conceived pregnancy**

NCT03426228

Statistical Analysis

1. Effects of IVF Therapy

Data analysis was performed with the Statistical Package for the Social Sciences (SPSS) software version 21.0 for Windows (SPSS, Chicago, IL). Parameters normality was confirmed with the Shapiro-Wilk test. Non-parametric Wilcoxon test for two related samples was conducted to assess changes at baseline vs. post-IVF treatment (12 weeks) within groups (pregnant or non-pregnant). Non-parametric Mann-Whitney U test for two independent samples was used to compare the two groups pregnant vs. non-pregnant, at baseline and at 12 weeks. Bivariate correlation was used to determine correlations between the different anthropometric and metabolic parameters at week 12. Data from the two groups were analysed separately. Linear regression was used for assessment of association of change in glucose level at 12 weeks (dependent variable) with change in other anthropometric and biochemical parameters, separately for each group. Changes in glucose and insulin levels (and the resulting HOMA-IR) throughout IVF therapy (baseline, 2, 4 and 12 weeks) were determined with the mixed model for repeated measures test. Significance level was set at $p < 0.05$ and 95% confidence interval.

2. Anthropometrics and Biomarkers of Gestational Diabetes Mellitus (GDM)

In the pregnant group, the Mann-Whitney U test for two independent samples was used to compare data at baseline with 12 weeks, for comparison between women who later developed GDM to the non-GDM group. Changes at baseline, 4 and at 12 weeks were assessed by non-parametric Wilcoxon test (two related samples) within groups (future GDM or non-future GDM women). Predictors of GDM were assessed using binary logistic regression, adjusting for the following variables: age and history of PCOS.

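### The only stated pregnant versus non-pregnant comparison is a rank test at each time point, with no baseline adjustment and no effect estimate, and the normality statement does not explain the choice

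*SAP*

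**What the plan says.** SAP section 1 (Effects of IVF Therapy) sets out the following.

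- **Distribution check, followed directly by a rank test:** "Parameters normality was confirmed with the Shapiro-Wilk test. Non-parametric Wilcoxon test for two related samples was conducted". The SAP does not say which variables, time points, groups or residuals were tested, what was found, or how the result decides the method.
- **Within groups:** "Non-parametric Wilcoxon test for two related samples was conducted to assess changes at baseline vs. post-IVF treatment (12 weeks) within groups".
- **Between groups:** "Non-parametric Mann-Whitney U test for two independent samples was used to compare the two groups pregnant vs. non-pregnant, at baseline and at 12 weeks".
- **Association:** "Bivariate correlation was used to determine correlations between the different anthropometric and metabolic parameters at week 12", with the type of correlation not named. Then "Linear regression was used for assessment of association of change in glucose level at 12 weeks (dependent variable"), fitted separately in each group.
- **Repeated measures:** glucose, insulin and HOMA-IR over baseline and weeks 2, 4 and 12 "were determined with the mixed model for repeated measures test". No group term, covariate, covariance structure or scale is given.
- **Level:** one closing line sets p < 0.05 and a "95% confidence interval".

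Table 1 in Protocol section 2.7 shows HbA1c, TSH, lipids, adiponectin, LBP and body weight measured at baseline and week 12. Protocol section 2.4 defines the two groups by the pregnancy test at 4 weeks. Protocol section 2.5 describes a convenience sample. Neither document gives a sample size.

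**The concern.** There are two issues, and the second matters more.

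First, a reader cannot tell why rank tests were chosen. If *confirmed* means that the variables looked normal, the rank tests are unexplained. If it means that normality was checked and failed, the sentence says the opposite of what was found. No rule links the check to the tests.

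Second, the first objective in Protocol Chapter 1 concerns the effect of hormonal therapy on metabolic and inflammatory status. The non-pregnant women, who stop therapy at week 4, are the only comparison group. The informative contrast is therefore how the two groups differ at week 12 given where each woman started. The plan does not state one. Two snapshot Mann-Whitney tests do not supply it. Nor do two separate within-group Wilcoxon tests, because a significant change in one group and a non-significant change in the other is not a test of the difference. For the six marker types that Table 1 lists only at baseline and week 12, no other between-group analysis is stated.

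At stake are a group difference that may simply be the baseline difference carried forward, precision lost although the baseline sample was taken, and a p-value with no effect size.

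**Working it through.** **Plan's own figures.** The documents give no power, SD, correlation or sample size, so there is nothing to reproduce. Everything below rests on assumed inputs: correlation ρ between baseline and week 12, two-sided α = 0.05, equal groups.

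**1. Coverage of the group contrast**

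| Marker | Stated pregnant vs non-pregnant analysis | Uses own baseline? | Estimate and CI named? |
|---|---|---|---|
| HbA1c, TSH, lipids, adiponectin, LBP, weight | Mann-Whitney at baseline and at week 12 | No | No |
| Glucose, insulin, HOMA-IR | The same, plus a mixed model with no stated group term | Unclear | Unclear |

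**2. Cost of ranks alone.** If data are normal, the asymptotic efficiency of Mann-Whitney relative to the t-test is 3/π = 0.955. Power becomes Φ((1.960 + 0.842)·√0.955 − 1.960) = 78.2% where the t-test has 80%. That is about 2 points.

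**3. Cost of omitting baseline.** The residual variance fraction after adjustment is 1 − ρ². Where ANCOVA has 80% power, an unadjusted week-12 t-test has Φ(2.802·√(1 − ρ²) − 1.960). For Mann-Whitney, multiply 1 − ρ² by 0.955.

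| ρ | 1 − ρ² | Variance removed | t-test power | Mann-Whitney power |
|---|---|---|---|---|
| 0.3 | 0.91 | 9% | 76% | 74% |
| 0.5 | 0.75 | 25% | 68% | 66% |
| 0.7 | 0.51 | 49% | 52% | 50% |

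Most of the loss comes from omitting baseline, and its size depends on ρ.

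**4. Skewed data.** Simulated power (4,000 runs, 40 per group, ρ = 0.6, balanced baselines, effect set for 80% ANCOVA power on the normal scale):

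| Data | Mann-Whitney | t-test | ANCOVA, raw scale | ANCOVA, log scale |
|---|---|---|---|---|
| Normal | 58% | 61% | 80% | n/a |
| Log-normal | 56% | 43% | 55% | 79% |

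With skewed data, ranks beat the raw t-test and match raw-scale ANCOVA. The gain comes from adjusting for baseline on a suitable scale.

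**5. Baseline imbalance.** Suppose the groups differ at baseline by δ SD and there is no week-12 effect given baseline. The expected week-12 difference is ρδ SD. Mann-Whitney then rejects with probability of about Φ(c − 1.960) + Φ(−c − 1.960), where c = ρδ·√(n/2)·√0.955. With ρ = 0.6:

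| δ | n per group | ρδ | c | Rejection, formula | Rejection, simulated |
|---|---|---|---|---|---|
| 0.3 | 50 | 0.18 | 0.88 | 14% | 13% |
| 0.3 | 80 | 0.18 | 1.11 | 20% | 20% |
| 0.5 | 50 | 0.30 | 1.47 | 31% | 29% |
| 0.5 | 80 | 0.30 | 1.85 | 46% | 45% |

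ANCOVA stayed at 4-6% in the same simulations. The Mann-Whitney test at baseline does not repair this: it may flag an imbalance, but it does not remove it.

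**The case against.** The strongest reply is that the normality sentence is loose wording for *checked*. Rank tests then follow naturally, and the regression and mixed models are unaffected. Much of this stands. A reader might infer that the methods contradict each other, because rank tests sit beside normal-theory models. The documents do not support that. The SAP speaks of the parameters, meaning the variables themselves, whereas the models need well-behaved residuals. What remains is that the sentence, as written, does not explain the choice.

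Three further inferences also go too far.

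- *The models were fitted to untransformed data and have unreliable standard errors.* The SAP neither states nor excludes a transformation. With log-normal data and no true effect, raw-scale ANCOVA rejected 4.7%, 4.9% and 4.2% of the time at 20, 50 and 80 per group, close to nominal. The mixed model was not checked in this way.
- *The SAP promises an interval for every test.* Its closing line only sets a level. The regression, mixed and logistic models can give intervals; the gap is confined to the rank tests.
- *Baseline data are discarded.* The within-group tests, the change-in-glucose regression and the repeated-measures model all use baseline. It is missing only from the stated group contrast.

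It can also be said that gains from ANCOVA are a randomised-trial argument, and that in these groups adjustment estimates a different, conditional contrast. That is correct. With imbalance the precision gain shrinks, and the adjusted result must be read as conditional on baseline. But baseline is measured before the week-4 test that forms the groups, so it is a legitimate covariate, and non-randomised groups make adjustment more necessary, not less.

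**Conclusion.** The point holds in a limited form. The normality statement does not account for the rank tests. The stated pregnant versus non-pregnant comparison is unadjusted, does not test the difference in change, and has no named estimate or interval. For the markers measured only at baseline and week 12 it is the only between-group analysis stated.

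Baseline adjustment would remove about 25-49% of residual variance at an assumed correlation of 0.5-0.7, but only 9% at 0.3. With a correlation of 0.6 and 50-80 women per group, also assumed, a baseline imbalance of 0.3 to 0.5 SD alone would make the week-12 Mann-Whitney significant in roughly 13-45% of studies. The documents do not show that such an imbalance exists.

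The use of ranks is not itself the fault: it costs about 2 power points if data are normal and can help if they are skewed. This should be changed because the remedy is cheap and uses data already collected. It does not show that the planned tests are invalid.

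**What to change.** 1. Compare the groups at week 12 by ANCOVA with the baseline value of the same marker as covariate, on the log scale where residuals are skewed. Report a difference, or a ratio of geometric means, with a 95% CI.
2. Keep Wilcoxon and Mann-Whitney as sensitivity analyses, each with a Hodges-Lehmann estimate and interval.
3. Rewrite the Shapiro-Wilk sentence to say what was tested, what was found, and how the result determined the method.
4. State whether the mixed model has group and group-by-time terms. Check the residuals of the regression and mixed models, and report any transformation.

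The cost is SAP wording and a modest re-analysis, with no new samples. Logged markers will be reported as ratios. The SAP is written in the past tense, so if the analysis is already done the new contrast must be labelled post hoc. Adjusting for baseline does not remove other confounding between women who conceive and women who do not, and the report should say so.
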